APPENDIX A: PERFORMANCE STATUS CRITERIA

ECOG Performance Status Scale		Karnofsky Performance Scale		
Grade	Descriptions	Percent	Description	
0	Normal activity. Fully active, able to carry on all pre-disease	100	Normal, no complaints, no evidence of disease.	
U	performance without restriction.	90	Able to carry on normal activity; minor signs or symptoms of disease.	
1	Symptoms, but ambulatory. Restricted in physically strenuous activity, but ambulatory and able		Normal activity with effort; some signs or symptoms of disease.	
1	to carry out work of a light or sedentary nature (e.g., light housework, office work).	70	Cares for self, unable to carry on normal activity or to do active work.	
2	In bed <50% of the time. Ambulatory and capable of all self-care, but unable to carry out		Requires occasional assistance, but is able to care for most of his/her needs.	
	any work activities. Up and about more than 50% of waking hours.	50	Requires considerable assistance and frequent medical care.	
2	In bed >50% of the time. Capable of only limited self-care, confined	40	Disabled, requires special care and assistance.	
3	to bed or chair more than 50% of waking hours.	30	Severely disabled, hospitalization indicated. Death not imminent.	
4	100% bedridden. Completely disabled. Cannot carry on any	20	Very sick, hospitalization indicated. Death not imminent.	
'1	self-care. Totally confined to bed or chair.	10	Moribund, fatal processes progressing rapidly.	
5	Dead.	0	Dead.	

APPENDIX B: MANAGEMENT ALGORITHMS

These general guidelines constitute guidance to the Investigator and may be supplemented by discussions with the IND Sponsor. The guidance applies to all immuno-oncology (I-O) agents and regimens.

A general principle is that differential diagnoses should be diligently evaluated according to standard medical practice. Non-inflammatory etiologies should be considered and appropriately treated.

Corticosteroids are a primary therapy for immuno-oncology drug-related adverse events. The oral equivalent of the recommended IV doses may be considered for ambulatory subjects with low-grade toxicity. The lower bioavailability of oral corticosteroids should be taken into account when switching to the equivalent dose of oral corticosteroids.

Consultation with a medical or surgical specialist, especially prior to an invasive diagnostic or therapeutic procedure, is recommended.

The frequency and severity of the related adverse events covered by these algorithms will depend on the immuno-oncology agent or regimen being used.

[figure not shown]

APPENDIX C: RESPONSE EVALUATION CRITERIA IN SOLID TUMORS (RECIST) 1.1 CRITERIA FOR EVALUATING RESPONSE IN SOLID TUMORS

RECIST version 1.1 will be used in this study for assessment of tumor response. While either CT or MRI may be used utilized, as per RECIST 1.1, CT is the preferred imaging technique in this study.

Disease Parameters

Measurable disease: Measurable lesions are defined as those that can be accurately measured in at least one dimension (longest diameter to be recorded) as \geq 20 mm by chest x-ray, as \geq 10 mm with CT scan, or \geq 10 mm with calipers by clinical exam. All tumor measurements must be recorded in millimeters (or decimal fractions of centimeters).

Note: Tumor lesions that are situated in a previously irradiated area might or might not be considered measurable unless there is evidence of progression in the irradiated site. Malignant lymph nodes. To be considered pathologically enlarged and measurable, a lymph node must be ≥15 mm in short axis when assessed by CT scan (CT scan slice thickness recommended to be no greater than 5 mm). At baseline and in follow-up, only the short axis will be measured and followed.

Non-measurable disease: All other lesions (or sites of disease), including small lesions (longest diameter <10 mm or pathological lymph nodes with ≥10 to <15 mm short axis), are considered non-measurable disease. Bone lesions, leptomeningeal disease, ascites, pleural/pericardial effusions, lymphangitis cutis/pulmonitis, inflammatory breast disease, and abdominal masses (not followed by CT or MRI), are considered as non-measurable.

Note: Cystic lesions that meet the criteria for radiographically defined simple cysts should not be considered as malignant lesions (neither measurable nor non-measurable) since they are, by definition, simple cysts.

'Cystic lesions' thought to represent cystic metastases can be considered as measurable lesions, if they meet the definition of measurability described above. However, if non-cystic lesions are present in the same subject, these are preferred for selection as target lesions.

Target lesions: All measurable lesions up to a maximum of 2 lesions per organ and 5 lesions in total, representative of all involved organs, should be identified as **target lesions** and recorded and measured at baseline. Target lesions should be selected on the basis of their size (lesions with the longest diameter), be representative of all involved organs, but in addition should be those that lend themselves to reproducible repeated measurements. It may be the case that, on occasion, the largest lesion does not lend itself to reproducible measurement in which circumstance the next largest lesion which can be measured reproducibly should be selected. A sum of the diameters (longest for non-nodal lesions, short axis for nodal lesions) for all target lesions will be calculated and reported as the baseline sum diameters. If lymph nodes are to be included in the sum, then only the short axis is added into the sum. The baseline sum diameters will be used as reference to further characterize any objective tumor regression in the measurable dimension of the disease.

Non-target lesions: All other lesions (or sites of disease) including any measurable lesions over and above the 5 target lesions should be identified as **non-target lesions** and should also be recorded at baseline. Measurements of these lesions are not required, but the presence, absence, or in rare cases unequivocal progression of each should be noted throughout follow-up.

Evaluation of Target Lesions

Complete Response (CR): Disappearance of all target lesions. Any pathological lymph nodes (whether target or non-target) must have reduction in short axis to <10 mm.

Partial Response (PR): At least a 30% decrease in the sum of the diameters of target lesions, taking as reference the baseline sum diameters.

Progressive Disease (PD): At least a 20% increase in the sum of the diameters of target lesions, taking as reference the smallest sum on study (this includes the baseline sum if that is the smallest on study). In addition to the relative increase of 20%, the sum must also demonstrate an absolute increase of at least 5 mm. (Note: the appearance of one or more new lesions is also considered progressions).

Stable Disease (SD): Neither sufficient shrinkage to qualify for PR nor sufficient increase to qualify for PD, taking as reference the smallest sum diameters while on study.

Evaluation of Non-Target Lesions

Complete Response (CR): Disappearance of all non-target lesions and normalization of tumor marker level. All lymph nodes must be non-pathological in size (<10 mm short axis).

Note: If tumor markers are initially above the upper normal limit, they must normalize for a subject to be considered in complete clinical response.

Non-CR/Non-PD: Persistence of one or more non-target lesion(s) and/or maintenance of tumor marker level above the normal limits.

Progressive Disease (PD): Appearance of one or more new lesions and/or *unequivocal progression* of existing non-target lesions. *Unequivocal progression* should not normally trump target lesion status. It must be representative of overall disease status change, not a single lesion increase.

Although a clear progression of "non-target" lesions only is exceptional, the opinion of the treating physician should prevail in such circumstances, and the progression status should be confirmed at a later time by the review panel (or Principal Investigator).

Evaluation of Best Overall Response

The best overall response is the best response recorded from the start of the treatment until disease progression/recurrence (taking as reference for progressive disease the smallest measurements

recorded since the treatment started). The subject's best response assignment will depend on the achievement of both measurement and confirmation criteria.

For Subjects with Measurable Disease (i.e., Target Disease)

Target Lesions	Non-Target Lesions	New Lesions	Overall Response	Best Overall Response when
				Confirmation is Required*
CR	CR	No	CR	≥4 wks. Confirmation**
CR	Non-CR/Non- PD	No	PR	
CR	Not evaluated	No	PR	≥4 wks.
PR	Non-CR/Non- PD/not evaluated	No	PR	Confirmation**
SD	Non-CR/Non- PD/not evaluated	No	SD	Documented at least once ≥4 wks. from baseline**
PD	Any	Yes or No	PD	
Any	PD***	Yes or No	PD	no prior SD, PR or CR
Any	Any	Yes	PD	

^{*} See RECIST 1.1 manuscript for further details on what is evidence of a new lesion.

Note: Subjects with a global deterioration of health status requiring discontinuation of treatment without objective evidence of disease progression at that time should be reported as "symptomatic deterioration." Every effort should be made to document the objective progression even after discontinuation of treatment.

Reference

E.A. Eisenhauer, P. Therasse, J. Bogaerts, L.H. Schwartz, D. Sargent, R. Ford, J. Dancey, S. Arbuck, S. Gwyther, M. Mooney, L. Rubinstein, L. Shankar, L. Dodd, R. Kaplan, D. Lacombe, J. Verweij. New response evaluation criteria in solid tumours: Revised RECIST guideline (version 1.1). Eur J Cancer. 2009 Jan;45(2):228-47.

^{**} Only for non-randomized trials with response as primary endpoint.

^{***} In exceptional circumstances, unequivocal progression in non-target lesions may be accepted as disease progression.

APPENDIX D: DESCRIPTION OF THE IRECIST PROCESS FOR ASSESSMENT OF DISEASE PROGRESSION

Assessment at Screening and Prior to RECIST 1.1 Progression

Until radiographic progression based on RECIST 1.1, there is no distinct iRECIST assessment.

Assessment and Decision at RECIST 1.1 Progression

In participants who show evidence of radiological PD by RECIST 1.1 the Investigator will decide whether to continue a participant on study treatment until repeat imaging is obtained using the criteria outlined in **Section 4.10.1**.

If the Investigator decides to continue treatment, the participant may continue to receive study treatment and the tumor assessment should be repeated 4 to 8 weeks later to confirm PD by iRECIST, per Investigator assessment.

Tumor flare may manifest as any factor causing radiographic progression per RECIST 1.1, including:

- Increase in the sum of diameters of target lesion(s) identified at baseline to \geq 20% and > 5 mm from nadir
 - Please note: the iRECIST publication uses the terminology "sum of measurements", but "sum of diameters" will be used in this protocol, consistent with the original RECIST 1.1 terminology.
- Unequivocal progression of non-target lesion(s) identified at baseline
- Development of new lesion(s)

iRECIST defines new response categories, including **iUPD** (unconfirmed progressive disease) and **iCPD** (confirmed progressive disease). For purposes of iRECIST assessment, the first visit showing progression according to RECIST 1.1 will be assigned a visit (overall) response of iUPD, regardless of which factors caused the progression.

At this visit, target and non-target lesions identified at baseline by RECIST 1.1 will be assessed as usual.

New lesions will be classified as measurable or non-measurable, using the same size thresholds and rules as for baseline lesion assessment in RECIST 1.1. From measurable new lesions, up to 5 lesions total (up to 2 per organ), may be selected as New Lesions – Target. The sum of diameters of these lesions will be calculated, and kept distinct from the sum of diameters for target lesions at baseline. All other new lesions will be followed qualitatively as New Lesions – Non-target.

Assessment at the Confirmatory Imaging

On the confirmatory imaging, the participant will be classified as progression confirmed (with an overall response of iCPD), or as showing persistent unconfirmed progression (with an overall response of iUPD), or as showing disease stability or response (iSD/iPR/iCR).

Confirmation of Progression

Progression is considered confirmed, and the overall response will be iCPD, if ANY of the following occurs:

- Any of the factors that were the basis for the initial iUPD show worsening
 - \circ For target lesions, worsening is a further increase in the sum of diameters of ≥ 5 mm, compared to any prior iUPD time point
 - For non-target lesions, worsening is any significant growth in lesions overall, compared to a prior iUPD time point; this does not have to meet the "unequivocal" standard of RECIST 1.1
 - o For new lesions, worsening is any of these:
 - An increase in the new lesion sum of diameters by ≥ 5 mm from a prior iUPD time point
 - Visible growth of new non-target lesions
 - The appearance of additional new lesions
- Any new factor appears that would have triggered PD by RECIST 1.1

Persistent iUPD

Progression is considered not confirmed, and the overall response remains iUPD, if:

- None of the progression-confirming factors identified above occurs AND
- The target lesion sum of diameters (initial target lesions) remains above the initial PD threshold (by RECIST 1.1)

Additional imaging for confirmation should be scheduled 4 to 8 weeks from the scan on which iUPD is seen. This may correspond to the next visit in the original visit schedule. The assessment of the subsequent confirmation scan proceeds in an identical manner, with possible outcomes of iCPD, iUPD, and iSD/iPR/iCR.

Resolution of iUPD

Progression is considered not confirmed, and the overall response becomes iSD/iPR/iCR, if:

- None of the progression-confirming factors identified above occurs, AND
- The target lesion sum of diameters (initial target lesions) is not above the initial PD threshold.

The response is classified as iSD or iPR (depending on the sum of diameters of the target lesions), or iCR if all lesions resolve.

In this case, the initial iUPD is considered to be pseudo-progression, and the level of suspicion for progression is "reset". This means that the next visit that shows radiographic progression,

whenever it occurs, is again classified as iUPD by iRECIST, and the confirmation process is repeated before a response of iCPD can be assigned.

Detection of Progression at Visits After Pseudo-progression Resolves

After resolution of pseudo-progression (ie, achievement of iSD/iPR/iCR), iUPD is indicated by any of the following events:

Target lesions

O Sum of diameters reaches the PD threshold ($\geq 20\%$ and ≥ 5 mm increase from nadir) either for the first time, or after resolution of previous pseudo-progression. The nadir is always the smallest sum of diameters seen during the entire trial, either before or after an instance of pseudo-progression.

• Non-target lesions

- o If non-target lesions have never shown unequivocal progression, their doing so for the first time results in iUPD.
- o If non-target lesions had shown previous unequivocal progression, and this progression has not resolved, iUPD results from any significant further growth of non-target lesions, taken as a whole.

• New lesions

- New lesions appear for the first time
- Additional new lesions appear
- O Previously identified new target lesions show an increase of ≥ 5 mm in the new lesion sum of diameters, from the nadir value of that sum
- o Previously identified non-target lesions show any significant growth

If any of the events above occur, the overall response for that visit is iUPD, and the iUPD evaluation process (see Assessment at the Confirmatory Imaging above) is repeated. Progression must be confirmed before iCPD can occur.

The decision process is identical to the iUPD confirmation process for the initial PD, except in one respect. If new lesions occurred at a prior instance of iUPD, and at the confirmatory scan the burden of new lesions has increased from its smallest value (for new target lesions, their sum of diameters is ≥ 5 mm increased from its nadir), then iUPD cannot resolve to iSD or iPR. It will remain iUPD until either a decrease in the new lesion burden allows resolution to iSD or iPR, or until a confirmatory factor causes iCPD.

Additional details about iRECIST are provided in the iRECIST publication[40].

Table 3: Comparison between RECIST 1.1 and iRECIST

	RECIST 1.1	iRECIST		
Definitions of disease:	Measurable are diameters greater	No change from RECIST 1.1		
numbers, sites and	than 10 mm (15 for nodes			
target or non	maximum of 5 (2 per organ)			
CR, PR or SD	Cannot have met criteria for progression	Can have had iUPD (more than once) but not iCPD before iCR, iPR or iSD		
Confirmation of CR or PR	Only in non-randomized studies	As per RECIST 1.1		
Confirmation of SD	Not required	As per RECIST 1.1		
New lesions	Progression: recorded but not measured	iUPD but only becomes iCPD if on the next scan there are new lesions or the size increases by greater than 5 mm		
Confirmation of Progression Not required Re		Required		
Consideration of clinical status	Not required	Clinical stability considered at iUPD to decide treatment continuation		

Table 4: Trajectory of progression in iRECIST

Target Lesions: iCR, Non-target: iCR, no new lesions	iCR	iCR
Target lesions: iCR, Non- target: non iCR/non iUPD, no new lesions	iPR	iPR
Target Lesions: iPR, Non- target: non iCR/non iUPD, no new lesions	iPR	iPR
Target lesions: iSD, Non- target: non iCR/non iUPD, no new lesions	iSD	iSD
Target lesions: iUPD with no change or with a decrease from the last time point, Nontarget: iUPD with no change or decrease from last time point, new lesions	NA	New lesions confirm iCPD if new lesions previously identified and increased in size (≥ 5 mm in sum of measures for new lesions or any increase for new lesion non-target) or increase in number. If no change is seen in new lesions assignment remains iUPD

Target lesions: iSD, iPR, iCR, non-target: iUPD, no new lesions	iUPD	Remains iUPD unless iCPD is confirmed by increase in the size of non-targets (does not need to meet RECIST 1.1 criteria)
Target lesions: iUPD, non-target: non iCR/non iUPD, no new lesions	iUPD	Remains iUPD unless iCPD confirmed on the basis of further increase ≥ 5 mm; otherwise stays as iUPD
Target lesions: iUPD, non-target: iUPD, no new lesions	iUPD	Remains iUPD unless iCPD confirmed on previously identified targets iUPD ≥ 5 mm or non-target iUPD
Target lesions: iUPD, non-targets: iUPD, new lesions	iUPD	Remains iUPD unless iCPD confirmed by increase of ≥ 5 mm previously identified target, or non-target or an increase in size or number of new lesions
Target lesions non iUPD or progression, non-targets: non iUPD or progression, new lesions	iUPD	Remains iUPD unless iCPD confirmed by increase in size or number of new lesions previously identified.

Target lesions, non-target lesions and new lesions are defined according to RECIST 1.1 criteria: if no pseudoprogression occurs, RECIST 1.1 and iRECIST categories for CR, PR and SD are the same. * Previously identified in the assessment prior to this time point. 'I' indicates immune responses assigned using iRECIST

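### Appendix D classifies a first new lesion at the confirmatory scan two ways once baseline lesions are no longer iUPD: iCPD by the text, iUPD by the last row of Table 4 (exploratory iORR and iPFS only)

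*Combined protocol and SAP*

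**What the plan says.** Appendix D, Confirmation of Progression, opens with "Progression is considered confirmed, and the overall response will be iCPD, if ANY of the following occurs". One of the listed conditions is "Any new factor appears that would have triggered PD by RECIST 1.1". The two other outcomes described there, persistent iUPD and resolution of iUPD, each require that no confirming factor has occurred.

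A new lesion counts as progression under RECIST 1.1 in both appendices. Appendix C states that "the appearance of one or more new lesions is also considered progressions". Appendix D lists new lesions as a cause of RECIST 1.1 progression, separate from target and non-target growth.

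Table 4, last row, covers target and non-target lesions that are not in iUPD, with new lesions present. Its entry is "Remains iUPD unless iCPD confirmed by increase in size or number of new lesions previously identified". A footnote to the table explains that the phrase about earlier identification refers to the assessment before the current one.

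Table 3, new-lesions row, describes a new lesion under iRECIST as "iUPD but only becomes iCPD if on the next scan there are new lesions or the size increases by greater than 5 mm". On response after progression, the same table says a patient "Can have had iUPD (more than once) but not iCPD before iCR, iPR or iSD".

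Section 10.3 dates iPFS at iUPD if the next scan, 4 to 8 weeks later, confirms progression. It lists iORR among the exploratory endpoints.

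**The concern.** The text and Table 4 are both offered as the way to label a visit, and for one recognisable scan they give opposite labels. iUPD and iCPD lead to different endpoint results. An iCPD closes the door to a later iCR, iPR or iSD, and it turns the preceding iUPD into an iPFS event. An iUPD does neither.

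The situation can arise in this trial. Section 4.10.1 allows treatment beyond RECIST 1.1 progression, and Appendix D then calls for repeat imaging, read by the investigator. Two readers could follow different parts of the same appendix and label identical scans differently. If the choice is left until the data are in, it will be made with the patients' later outcomes already known.

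**Working it through.** The plan states no figure on this point, so the check sets the rules side by side. In each case the first iUPD came from target or non-target growth, and a new lesion is first seen at the confirmatory scan.

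**Step 1: what the text gives.** One listed condition is enough. A new lesion is a RECIST 1.1 progression factor. Persistent iUPD and resolution are excluded once a confirming factor has occurred. The text therefore gives iCPD whatever the target sum does.

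**Step 2: what the tables give.** The column headings of Table 4 are not visible in the available text. One column has entries such as NA and iUPD, and the other speaks of remaining iUPD, so I read the latter as applying to patients with a prior iUPD.

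| Baseline lesions at the confirmatory scan | Text | Table 4 | Table 3, read literally |
|---|---|---|---|
| (a) No longer iUPD | iCPD | iUPD (last row: a first-seen lesion was not identified before) | iUPD |
| (b) One category still iUPD | iCPD | No matching row; the single-category rows are labelled as having no new lesions | iUPD |
| (c) Target and non-target both still iUPD | iCPD | Ambiguous | iUPD |

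In case (c), one row accepts an increase in the number of new lesions. Going from none to one can be read as such an increase, which agrees with the text. The other row, for iUPD unchanged or decreased, says "New lesions confirm iCPD if new lesions previously identified and increased in size" and then adds an increase in number, so it can be read either way.

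Case (a) is a direct contradiction between the text and Table 4. Case (b) is a gap and case (c) an ambiguity.

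**Step 3: whether another rule settles case (a).** Later in Appendix D, new lesions appearing for the first time give iUPD, but only after pseudo-progression has resolved. By the text nothing has resolved here, because a confirming factor has occurred. That rule does not apply.

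**Step 4: consequence for the endpoints in case (a).**

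| | iPFS (Section 10.3) | Later iPR in iORR (Table 3) |
|---|---|---|
| By the text (iCPD) | Event, dated at the first iUPD | Barred |
| By Table 4 (iUPD) | Next scan has not confirmed; no event at that point | Still possible |

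**Step 5: size per patient.** With a full cohort of 32, each later iPR counted or barred changes iORR by 1/32 = 3.1 percentage points. If there were one to three such responders, an assumption for scale only, the range would be 3.1 to 3/32 = 9.4 points.

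**Step 6: primary analysis.** Section 10.1 defines ORR by RECIST 1.1, so the iRECIST label does not enter it. As a side check, the Simon design (18 + 14 patients, at least 1 and then at least 4 responses) has an exact type I error of 0.072 and power of 0.901. This is consistent with the stated 0.1 limit and 90%.

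**The case against.** The strongest reply is that the text is explicit and operative, and the tables only summarise it. Table 3 is titled as a comparison of RECIST 1.1 with iRECIST. Its new-lesions row can be read as covering only a new lesion that is the first cause of iUPD, and its mention of new lesions on the next scan can even be read as agreeing with the text. This stands for Table 3, so I do not count it as a firm contradiction.

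The same reply can be tried on Table 4's last row: its wording may presuppose that new lesions caused the earlier iUPD. This is possible, but the row does not say so. Its description, baseline lesions not in iUPD with new lesions present, fits case (a) exactly. A reader who looks up the scan there will record iUPD. The lost column headings, and a footnote whose anchor cannot be seen, leave some doubt about the layout but do not change the words of the row.

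A reader might infer that Tables 3 and 4 keep every first new lesion at iUPD. The documents do not support that: case (b) has no row, one row in case (c) can agree with the text, and Table 3 has the narrower reading above.

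A reader might also put a head count on the problem. Assuming 10 to 16 re-scanned patients of 32, with 15% to 30% in this situation, gives 10 × 0.15 = 1.5 to 16 × 0.30 = 4.8 patients per cohort. None of these inputs is in the documents. Even then, iORR moves only through later responders. Applying the design rates of 5% and 20% as a rough assumption gives 1.5 × 0.05 ≈ 0.1 to 4.8 × 0.20 ≈ 1.0 responder per cohort.

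Finally, a reader might infer that iPFS shifts by at least one 4-to-8-week interval. Section 10.3 does not show this. If a later scan confirms, the event might still be dated at the first iUPD, and the shift would be zero.

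**Conclusion.** The contradiction is real but narrow. When iUPD came from target or non-target growth, and at the confirmatory scan the baseline lesions are no longer iUPD but a first new lesion appears, the Appendix D text gives iCPD and Table 4's last row gives iUPD. Table 4 has a gap where one baseline category is still iUPD and is ambiguous where both are.

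The label decides whether an iPFS event is counted at the first iUPD and whether a later iPR can count. The size is 3.1 percentage points of iORR per affected responder in a full cohort of 32. The number of such patients is unknown, and no minimum effect on iPFS timing can be derived. The conclusion rests on reading Table 4's last column as the one for patients with a prior iUPD.

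Only the exploratory iORR and iPFS are affected, so the severity is minor.

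**What to change.** Before any iRECIST analysis, reconcile the Confirmation of Progression text with Tables 3 and 4, so that one stated rule covers a first new lesion at the confirmatory scan when iORR and iPFS are derived. The simplest route has three parts:

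- Conform Table 4's last row to the explicit text for the case where the earlier iUPD came from target or non-target growth.
- State that Table 3's new-lesions row concerns a new lesion that is the first cause of iUPD.
- State that the text governs endpoint derivation. This also closes the missing-row case and the ambiguous case.

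The change sets response classification for analysis only. Table 3 also links iUPD to the decision on continuing treatment, and this fix sets no rule on that.

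The cost is wording in one appendix, with no new scans or data.
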